1. Postmenopausal women, defined by lack of a menstrual period for an entire year or confirmed by physician 2. 18-80 years of age 3. Able to speak and read English 4. Completed a minimum of 8 years of education 5. Diagnosed with stage 0, I, II, or IIIa breast cancer, confirmed by medical record 6. Within 2 years post-completion of primary treatment 7. Will be at least two weeks post-breast conserving surgery or three weeks post-breast conserving surgery with sentinel lymph node biopsy or four weeks post-mastectomy at the start of participation.

Exclusion criteria:

1. Prior treatment with cancer chemotherapy, central nervous system radiation, or intrathecal therapy 2. Prior cancer involving the central nervous system 3. Clinical evidence of metastatic disease 4. Any of the following breast cancer surgery complications unless approved by the participant's health care provider: persistent seroma requiring aspiration, wound dehiscence, infection, prolonged drain output, lymphedema 5. Reconstructive surgery unless approved by the participant's health care provider 6. Any significant medical condition that would preclude them from exercising (e.g., uncontrolled diabetes, congestive heart failure, angina, uncontrolled arrhythmia or other symptoms that indicate increased risk for an acute cardiovascular or

Research activities:

Participants: We plan to recruit up to 350 postmenopausal women with early-stage breast cancer: up to 127 will undergo an exercise intervention in this 6-month study described below and up to 127 will be enrolled in an usual care arm. A subsample of women who are randomized will participate in the neuroimaging component of the study (n=150; 75/group).

Locations: Recruitment will take place at St. Clair Budway Surgical Associates and Magee-Women's Hospital of UPMC, Comprehensive Breast Care Center at UPMC Passavant-Cranberry, UPMC South Hills, UPMC McKeesport and Magee Woman care Center in Monroeville. Data collection will take place in participants' homes, at the University of Pittsburgh School of Nursing and Sennott Square or Healthy Lifestyle Institute offices in Oak Hill. The exercise intervention will take place at Sennott Square, Baierl Family YMCA, Sampson Family YMCA, and JCC South Hills Branch or Healthy Lifestyle Institute offices in Oak Hill; alternatively, a participant may exercise in her home or other location of her choosing. MRI Imaging will take place at Carnegie Mellon University SIBR.

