Informed Consent: Written informed consent will be obtained from the participant prior to any study-specific activities either in person or remotely.

Assessments: Participants will complete a series of assessments at two timepoints; Time 1(baseline) will occur up to 2 years post-completion of primary treatment and before randomization and initiation of the exercise intervention/usual care. Time 2 will occur approximately within 1 month of completion of the intervention (or 7 months post-Time 1). Data collection at each timepoint will be composed of behavioral assessments, blood samples, neuroimaging and objective measures of physical activity and fitness. We will also objectively evaluate physical activity at 3 time points during participation (approximately every 5 weeks). For participants who agree to additional follow-up via the addendum consent form, Time 3 will take place approximately 6 months post Time 2 and will consist of blood work, fitness testing and behavioral testing as described below. We will also objectively evaluate physical activity at midway (3 months) between Time 2 and Time 3 as well as at Time 3. Participants will also be asked to maintain their edema cap and REDCap diaries during this time. Participants may be asked to complete assessments in two separate sessions at both TP1 and TP2. During one visit (which includes fitness testing), blood samples (approximately 30cc or 6 teaspoons) will be collected for biobanking for future evaluation of the relationships of biomarkers (including genetic biomarkers) with cognitive function, exercise, brain health and symptoms. Blood samples will be transported immediately, under conditions appropriate for preservation of the blood, and stored before the end of the day of testing. Samples will be maintained in a -80°C freezer in the Victoria building under the control of the principal investigators of this research project and will be maintained indefinitely. In the event that we need to send samples to a different facility outside of the University of Pittsburgh for analysis in the future, no identifying information will accompany the sample. Participants will be asked questions prior to the blood draw to determine any factors which may affect the findings. If a recent illness is noted, or certain other factors as noted on the form, are found, the participant may not be eligible for a blood draw at this visit. In this event, we will attempt to collect the blood at another time, either during a subsequent visit or other agreed upon time. Fitness will be objectively measured at Time 1 and Time 2. This test takes 15-30 minutes to complete. Subjects will be given exercise testing instructions regarding proper clothing and footwear and will be told to abstain from caffeine or nicotine 2 hours prior to the physical activity/fitness assessment. When participants report to the laboratory (Sennott Square) for the fitness assessment they will first be acquainted with the equipment, allowed to ask any questions, and get comfortable with walking on a treadmill. Before the test begins, the participant will get familiar with wearing the mouthpiece and nose clips or facemask required during the test in order to measure cardiovascular fitness. This helps to reduce anxiety associated with exercise and fitness testing. Cardiovascular fitness testing consists of progressively increasing exercise intensity while the subjects exhaled air is collected via a mouthpiece that is connected to a gas exchange chamber via a breathing tube. A comfort fitted head gear supports the mouthpiece. This reduces the effort of the participant to keep the mouthpiece in the correct position throughout the test. Alternatively, the participant may wear a facemask. The gas chamber that is being used is the Parvo Medics True one 2400 metabolic cart, which is one of the most widely accepted systems in scientific research. Next we will provide the participant with adequate warm-up and stretching which will be monitored by the exercise physiologist. After 5-10 minutes of warm-up, the participant will walk on a motor-driven treadmill at a constant speed with increasing increments of the incline. We will conduct a submaximal vo_2 fitness test which estimates the maximal oxygen capacity for the individual without reaching an exhaustive level. The sub-maximal graded exercise test is a modified Balke protocol in which the speed remains constant and grade is increased 1% each minute. This protocol has been used extensively in the literature for fitness training for both normal, at-risk, and impaired populations. Verifying maximal vo_2 is difficult in at-risk

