
matches the letter on the previous trial (1-back) or the letter two trials previously (2-back). We will employ FSL software with standard preprocessing steps including motion correction, temporal filtering, and spatial smoothing and a sample-specific template for registration.^{75,156,157} We will also use Psychophysiological Interaction (PPI) analyses to examine changes in functional connectivity between regions during task performance.

Randomization: After completing the baseline assessments, subjects may be randomized into one of two groups: (1) Aerobic Exercise Intervention or (2) Usual Care. Subjects will be randomly assigned via a computer using a minimization algorithm with equal allocation to one of two treatment groups: 1) exercise intervention, or 2) usual care. Use of a minimization algorithm will insure treatment balance on two three factors: 1) age at study entry (<60, >60 to <70, >70 years) (since age is associated with reduced fitness, cognition, and brain measures), and 2) baseline levels of cognitive function, particularly executive function (based on the composite mean Z-score, <-0.5, > -0.5 to < +0.5, > +0.5), and 3) the time since primary cancer treatment (<= 6months, >6 months to 12 months). Minimization is a form of adaptive treatment allocation in which the probability of assignment to the treatment groups does not remain constant, but is determined by the current balance and/or composition of groups. In this study, the treatment assignment probability will be adjusted in response to the marginal distributions of categories of age at entry and baseline executive function such that the marginal distributions of these categories will be approximately equal between treatment groups. Treatment group assignment will be generated and stored in a secured database. Aerobic

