
person exercise, as described above, will be the preferred method for intervention delivery. However, participants may also exercise at their home, or other location of their choosing, as needed. When exercising at home, participants will be in contact with a study trainer at least weekly. Participants will receive guidance and coaching related to their exercise sessions - either in real-time or other time as to be accommodating as possible to the research participants. Heart rate during exercise sessions will be monitored via study-provided monitors and will be reported to trainers by the participant. Participants may be provided with online resources/videos for exercise (such as Be Fit Pitt) or may be encouraged to use an exercise resources available to them (such as owned exercise equipment, gym memberships, indoor or outdoor walking, etc.)

Usual Care Group: will not withhold physical activity or limit physical activity in the usual care group but instead will let them engage in activity in the same manner as if they were not part of an active intervention.

Statistical Plan

Randomization: Subjects will be randomly assigned via a computer using a minimization algorithm with equal allocation to one of two treatment groups: 1) exercise intervention, or 2) usual care. Use of a minimization algorithm will insure treatment balance on two factors: 1) age at study entry (<60, >60 to <70, >70 years) (since age is associated with reduced fitness, cognition, and brain measures), and 2) baseline levels of cognitive function, particularly executive function (based on the composite mean Z-score, < -0.5, > -0.5 to < +0.5, > +0.5). Minimization is a form of adaptive treatment allocation in which the probability of assignment to the treatment groups does not remain constant but is determined by the current balance and/or composition of groups. In this study, the treatment assignment probability will be adjusted in response to the marginal distributions of categories of age at entry and baseline executive function such that the marginal distributions of these categories will be approximately equal between treatment groups. Treatment group assignment will be generated and stored in a secured database.

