Data analysis: Preliminary Analyses. Exploratory analyses will be performed for data description and screening for anomalies (e.g., outliers, nonnormality). This will be done to: 1) describe univariate and bivariate distributions; 2) identify group imbalances and associations between dependent variables and suspected covariates/ confounders; 3) evaluate missing data; and 4) check for violation of statistical assumptions. If assumptions are violated, data transformations or more statistically robust procedures will be considered. Covariates/ confounders will be included in models secondarily and their effects on primary predictors/factors will be evaluated. The randomness of missing data will be investigated using available information on subject characteristics to help discern patterns in missing data, identify possible missing data mechanisms and inform strategies to handle missing data. If the data are ignorable missing, the estimation procedures to be used will produce unbiased estimates while allowing us to retain observations with missing values on the outcome variables. If needed, multiple imputation would be used to impute missing values on covariates. If the data are not ignorable missing, we may use selection or pattern mixture modeling to investigate the sensitivity of results.

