factor, while treatment assignment will be a between-subjects factor, with an interaction between time and group. Each derived cognitive domain composite will be modeled separately and interaction terms will be included to test our hypothesis that executive, memory, and attention domains will be more affected than other domains. We will consider baseline cognitive function values both as an assessment point and as a possible covariate in analyses. Fixed and/or time-dependent covariates may be included to adjust for group imbalances or variables related to the dependent variables. Standard fit indices will also be used to identify the most appropriate covariance structure. F-tests will test the main and interaction effects included in the model. Individual regression parameters will be computed and reported with standard errors to yield confidence intervals. For each model, residual analysis will be conducted to identify sources of model misspecification, outliers and influential observations. Sensitivity analyses will be performed to discern the impact of influential cases on results. To test specific hypotheses, linear contrasts will be specified and estimated in the repeated measures model to compare changes from follow-up to baseline values between groups. Wald t-statistics will be used to test each contrast. Marginal modeling with generalized estimating equations will also be used as it tends to be more robust to misspecification of the covariance structure and violations in normality assumptions. Results from each modeling approach will be compared via sensitivity analyses.

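### The Randomization text lists three minimization factors, the assignment rule and the Statistical Plan name two, and the third factor has no level for eligible women more than 12 months after treatment

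*Combined protocol and SAP*

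**What the plan says.** Two places in the combined protocol and SAP describe the allocation.

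- **Randomization (protocol part).** Minimization is to secure balance on age, baseline executive function and a third item, "the time since primary cancer treatment (<= 6months, >6 months to 12 months". Later in the same paragraph the assignment probability is to be "adjusted in response to the marginal distributions of categories of age at entry and baseline executive function". Time since treatment is not in that rule.
- **Statistical Plan, Randomization.** "Use of a minimization algorithm will insure treatment balance on two factors". The two listed are age and executive function, and the same two-factor assignment rule follows.

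Eligibility runs further than the third factor's levels. The inclusion criteria admit women "Within 2 years post-completion of primary treatment". The Assessments text says that baseline "will occur up to 2 years post-completion of primary treatment and before randomization".

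On the analysis side, one purpose of the Preliminary Analyses is to "identify group imbalances and associations between dependent variables" and suspected confounders. That section then commits to entering covariates at a secondary stage. The Analysis Plan for Aim 1 says: "We will consider baseline cognitive function values both as an assessment point and as a possible covariate in analyses". It permits, but does not require, further covariates. No section names the minimization factors as terms in the primary Aim 1 model.

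**The concern.** A reader cannot reconstruct the allocation scheme. One passage promises balance on a factor that no written assignment rule uses, and the Statistical Plan omits the factor altogether. The factor as printed also cannot classify every eligible woman: someone 18 months after treatment may be randomized but belongs to neither level, and no coding rule is given.

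This carries into the analysis. A minimized trial is normally analysed with its minimization factors in the model. Here the factor list is contradictory and the covariate set is left to be chosen after the data are inspected, so the analyst cannot tell which design factors the primary comparison should carry.

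**Working it through.** **1. The passages side by side**

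| Item | Randomization (protocol part) | Statistical Plan |
|---|---|---|
| Factors listed | 3 | 2 |
| Factors in the assignment rule | 2 | 2 |
| Levels for time since treatment | up to 6 months; over 6 to 12 months | none |

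The protocol paragraph prints both two and three as the count, perhaps because a strikethrough was lost. The conflict does not rest on those words: the third factor is written out with its levels, and neither rule uses it.

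**2. Coverage of the levels.** Months 0 to 6 fall in level 1 and months over 6 to 12 in level 2. Values such as 12.1, 18 or 24 months fall in no level. The uncovered part is (24 − 12)/24 = 50% of the eligible window by time. The share of women in it is not given. A lost comparison sign would not explain the gap, because the list closes at 12 months.

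**3. How much balance is at stake.** The plan gives no figure to reproduce, so this is an illustration. From the documents: equal allocation, and a ceiling of 127 per arm ("up to 127 will undergo an exercise intervention", and the same number for usual care), so 254 in total. Assumed: a biased coin of 0.8, age in equal thirds, executive function split 31/38/31%, women up to 12 months split equally between the two printed levels, and the share p past 12 months.

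If time since treatment plays no part in assignment, the SD of the between-arm gap in that share is about √(2p(1 − p)/127). At p = 0.25 this is √(0.375/127) = 0.0543, or 5.4 percentage points. Simulation (10,000 trials per cell) gives, in percentage points:

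| Scheme | p = 5% | 10% | 25% | 50% |
|---|---|---|---|---|
| Chance formula | 2.74 | 3.76 | 5.43 | 6.27 |
| Two-factor rule | 2.70 | 3.71 | 5.37 | 6.21 |
| Third factor used, late women put in level 2 | 2.68 | 3.55 | 4.91 | 5.20 |

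If the third factor is used but skipped for late women, the SD is 2.0 to 2.7 points over these shares. With a complete three-level factor it is 1.2 to 1.4. The two-factor rule therefore does no better than chance on time since treatment.

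**4. Effect on the endpoint.** Suppose late women differ by 0.1, 0.3 or 0.5 SD in cognitive change (assumed). A one-SD gap at p = 0.25 then shifts the comparison by 0.0543 × 0.1, 0.3 or 0.5 = 0.005, 0.016 or 0.027 SD. The unadjusted standard error is √(2/127) = 0.1255 SD, so the shift is 4%, 13% or 22% of it, and that standard error already allows for it. Simulated type I error of the unadjusted test under the two-factor rule is 4.7 to 5.1% (40,000 trials per cell).

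**5. What adjustment does in the Aim 1 model.** Aim 1 treats time as a repeated factor and tests group by time, with baseline as one of the assessment points. A baseline factor entered only as a main effect shifts both of a woman's values equally and cancels from her change. With complete data the group-by-time contrast is unchanged. In one simulated two-timepoint dataset (n = 254, p = 25%, a gap of 9.4 points) the contrast was 0.3283 without the factor and 0.3283 with its main effect (standard error 0.1211 both times). It became 0.2998 only when a factor-by-time term was added.

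**The case against.** The strongest reply is that this is an incomplete text edit with little consequence. The assignment sentence is the same in both places, so it may simply not have been updated when the third factor was added, and the program may have used all three. That is fair. A reader might infer that the promised balance on time since treatment was not delivered, or that allocation was run wrongly. The documents support neither, because they do not show which scheme was programmed.

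A reader might also infer that covariate adjustment is purely optional. That goes too far: the Preliminary Analyses commit to entering covariates secondarily. What stands is that this commitment names no minimization factor and does not reach the primary model, and that the Aim 1 text is only permissive.

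Third, every driver of the illustrated effect is assumed. The brief description places the first assessment before endocrine therapy, so the share of women past 12 months could be low. The documents do not give it, which is why the range starts at 5%.

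None of these replies removes the conflict between the two factor lists or supplies a level for women past 12 months.

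**Conclusion.** The contradiction and the level gap are both real in the current text and should be corrected. The reason is that the allocation method and the primary model's design factors cannot be determined from the plan. Harm to the result has not been shown.

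It is tempting to read this as a threat to validity, but the documents do not support that. Allocation is random with equal probability overall under either scheme, so there is no systematic bias, and type I error is not inflated. If a three-level factor were used and then left out of the model, simulated type I error is 4.3 to 5.2%, slightly conservative where the factor is strongly prognostic.

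The size is a loss of balance: an SD of about 5 points against about 1.3 in the share past 12 months. This assumes 254 randomized, a 25% share and a coin of 0.8. The documents do not say how strongly time since treatment predicts cognitive change, so the endpoint effect can only be called probably small.

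**What to change.** 1. Make the Randomization paragraph and the Statistical Plan agree on the factors and levels the program actually used, from what date, and how women past 12 months were coded.
2. If time since treatment was not used, delete it from the Randomization paragraph. If it was, name it in the assignment rule and in the Statistical Plan. If randomization continues, add a level for more than 12 to 24 months for future assignments only. Do not write in a level that was never run.
3. Prespecify the minimization factors actually used in the primary Aim 1 model, in a form that reaches the change contrast. This means either factor-by-time terms in the repeated-measures model, or a follow-up model adjusted for baseline score and the factors. Main effects alone are not enough.
4. If time since treatment was not a factor, adjust for it, in the same form, in a sensitivity analysis.

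The cost is wording in two places, one program level if randomization is still open and the factor is kept, and a few model terms. No new data are needed: age and executive function are baseline items, and time since treatment must be known to apply the eligibility criterion.

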Analysis Plan for Aim 1. An "intent-to-treat" (ITT) approach will be used for data analysis. All subjects will be included in the groups to which they were assigned, regardless of adherence to protocol, treatment received, withdrawal or protocol deviation. Although this approach is recommended for efficacy analyses in Retaste sensitivity of the results assuming ITT will be explored using information collected regarding participant's adherence to the exercise intervention (e.g., protocol, amount of treatment received) as well as the amount of activity engaged in by the usual care group. The primary endpoint, changes in cognitive function, will be derived from normed (for age, education) composites of neuropsychological test scores (expressed as mean Z-scores).¹ (Table 2) The composite scores for the targeted cognitive function domains are empirically derived via exploratory factor analysis. Given the variation in scaling, test scores are converted to Z-scores related to an established cohort of age- and education-matched healthy women, and then averaged into composites, where negative scores indicate poorer cognitive function. Linear mixed-effects modeling with linear contrasts will be used to examine the effect of treatment assignment on cognitive function over time. When fitting models, time will be repeated within-subjects

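### The plan calls its estimation procedures unbiased under ignorable missingness, which does not hold in general for the supporting GEE analysis, so the mixed-model versus GEE comparison could mislead

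*Combined protocol and SAP*

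**What the plan says.** All of this is in the Statistical Plan of the combined protocol and SAP.

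- **Preliminary Analyses.** For ignorable missingness the claim is made without exception: "the estimation procedures to be used will produce unbiased estimates while allowing us to retain observations with missing values on the outcome variables". Imputation is confined to predictors: "If needed, multiple imputation would be used to impute missing values on covariates". Anything further is optional and reserved for the non-ignorable case: "If the data are not ignorable missing, we may use selection or pattern mixture modeling to investigate the sensitivity of results".
- **Aim 1 analysis plan.** The main method is stated as follows: "Linear mixed-effects modeling with linear contrasts will be used to examine the effect of treatment assignment on cognitive function over time". A second method follows: "Marginal modeling with generalized estimating equations will also be used as it tends to be more robust to misspecification of the covariance structure". The section then adds: "Results from each modeling approach will be compared via sensitivity analyses".
- **Role of baseline.** This is left open: "We will consider baseline cognitive function values both as an assessment point and as a possible covariate in analyses".

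The plan does not state a working correlation for the GEE, weights for the probability of being observed, imputation of missing outcomes, or how a difference between the two methods would be read.

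**The concern.** Ignorability is a likelihood concept. When missingness depends only on observed data, a likelihood-based mixed model with adequate mean and covariance structures gives valid estimates without modelling the dropout. Standard GEE is not a likelihood method. In general it needs data missing completely at random, or missingness that depends only on covariates in the model. A blanket statement about the planned procedures therefore gives GEE a property that it lacks as described.

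The stated reason for using GEE adds to the difficulty. Its robustness to a wrong covariance structure is a complete-data property. When dropout depends on an earlier outcome, the size of the GEE bias depends on the working correlation.

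What is at stake is how the comparison is interpreted. The two methods could differ because of dropout, and the difference could be taken as a sign of covariance or normality problems. A biased GEE result could also appear to corroborate an effect.

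**Working it through.** The documents give no dropout rate, SD, visit correlation or effect size, so there is no planned figure to reproduce. The check is of an estimator property under stated assumptions.

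**Inputs from the protocol.** Two main visits (TP1, and TP2 about 7 months later); up to 127 women per arm; target contrast is the between-group difference in change.

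**Assumptions.** Baseline Y1 is normal with mean 0 and SD 1. TP2 score Y2 has SD σ = 0.8, 1.0 or 1.2 and correlation ρ = 0.6 with baseline. In each arm 22% are missing at TP2. Missingness is logistic in Y1 with log-odds slope 0.8 or 1.2 per SD, the lower scorers in the exercise arm being more likely to leave. In the usual care arm the slope is the same, zero (one arm only), or reversed (opposite directions).

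**Formulas.** Let m be the mean baseline score of completers in an arm, and D = m(exercise) − m(usual care). Since E(Y2 | Y1) has slope ρσ:

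- Independence GEE compares observed TP2 means with all-subject TP1 means: bias = ρσ·D.
- Exchangeable GEE moves each TP2 mean back by α·m, where α is the completers' mean residual cross-product divided by the pooled residual variance: bias = (ρσ − α)·D.
- Maximum likelihood with unstructured covariance uses the fitted slope ρσ in place of α: bias = 0.

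**Numbers.** Integrating the logistic model over the normal baseline gives m = 0.159 at slope 0.8 and 0.215 at slope 1.2. Thus D is 0 with the same mechanism in both arms, 0.159 or 0.215 with one arm only, and 0.318 or 0.430 with opposite directions. Results below use unrounded D.

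| Pattern, slope | σ | Independence bias | α | Exchangeable bias |
|---|---|---|---|---|
| Same in both arms | any | 0 | – | 0 |
| One arm, 0.8 | 0.8 | 0.076 | 0.556 | −0.012 |
| | 1.0 | 0.095 | 0.585 | 0.002 |
| | 1.2 | 0.115 | 0.588 | 0.021 |
| Opposite, 0.8 | 0.8 | 0.153 | 0.541 | −0.019 |
| | 1.0 | 0.191 | 0.569 | 0.010 |
| | 1.2 | 0.229 | 0.572 | 0.047 |
| One arm, 1.2 | 0.8 | 0.103 | 0.545 | −0.014 |
| | 1.0 | 0.129 | 0.573 | 0.006 |
| | 1.2 | 0.155 | 0.576 | 0.031 |
| Opposite, 1.2 | 0.8 | 0.207 | 0.519 | −0.017 |
| | 1.0 | 0.258 | 0.545 | 0.024 |
| | 1.2 | 0.310 | 0.547 | 0.074 |

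Example (last row): independence 0.6 × 1.2 × 0.430 = 0.310; exchangeable (0.72 − 0.547) × 0.430 = 0.074.

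**Agreement with simulation.**

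- 300 trials of 127 per arm (true effect 0.30 SD, ρ = 0.6, 20–25% dropout) gave independence bias of +0.134 (one arm) and +0.261 (opposite). Exchangeable gave +0.006 and +0.023, and inverse-probability weighting +0.004 and +0.006. These match the σ = 1.0 rows at slope 1.2.
- 400 trials of 127 per arm with no true effect (ρ = 0.7, about 20% missing, slope 0.8, equal SDs, two-sided 5% assumed) gave type I error for independence GEE of 13% (one arm) and 40% (opposite). Exchangeable gave 5% and 7%. Mean bias of unstructured maximum likelihood was −0.005 and −0.002.

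**The case against.** The case for leaving the plan alone has five parts.

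1. **GEE is only a supporting analysis.** Aim 1 justifies it by covariance and normality, and the unbiasedness sentence is a generic remark in a preliminary section. It stands that the primary estimate does not depend on GEE. The sentence nevertheless makes no exception, and GEE is one of the procedures to be used.
2. **The large biases need an independence working correlation, which the plan never chooses.** This stands. A reader might infer from the robustness argument that independence is intended; the documents do not say so. Aim 1 lets fit indices guide the covariance structure, but does not say that this governs the GEE. The choice remains open.
3. **The dropout models are strong.** At slope 1.2, dropouts in the affected arm average 0.763 SD below the baseline mean and completers 0.215 above, a gap of about 0.98 SD. The corresponding gap at slope 0.8 is 0.564 + 0.159 = 0.72 SD. Nothing in the documents points to dropout in opposite directions. Some differential dropout is plausible, since only one arm is asked to exercise three days a week for six months, but that too is an assumption.
4. **The plan already allows baseline as a covariate.** With baseline in the model, and dropout depending only on baseline and arm, the bias disappears: baseline-adjusted regression was within about 0.004 SD of the truth in every simulated scenario. This stands, but the plan does not commit to that option.
5. **The mixed model has its own sensitivity.** With σ = 1.2 and opposite-direction dropout, a random-intercept model was biased by +0.042 (slope 0.8) and +0.061 (slope 1.2), much like exchangeable GEE. Ignorability alone is therefore not sufficient for the mixed model either, and the correction should name its covariance structure.

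**Conclusion.** The point holds as a minor correction. The unbiasedness statement is right for a likelihood-based mixed model with an adequate covariance structure and wrong in general for the GEE as described. That the GEE is unweighted is read from the absence of any weighting in the plan, which is the ordinary reading.

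Bias in the group-by-time contrast requires baseline-related dropout that differs between arms. Under the assumptions above it is about 0.08 to 0.31 SD with independence. With exchangeable it is at most about 0.02 SD for equal SDs and up to about 0.07 SD in size for unequal SDs.

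Two stronger readings are not supported. One is that any dropout related to baseline cognition makes the methods disagree: when the relation is the same in both arms, the bias is about zero. The other is that the primary result is compromised: the mixed-model estimate is unaffected by how GEE behaves, and only the comparison between the two is at risk.

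**What to change.** - In Preliminary Analyses, limit the unbiasedness statement to the mixed model, fitted with an unstructured covariance over the visits.
- In the Aim 1 plan, run the GEE check either with inverse-probability-of-observation weights or after multiple imputation of TP2 outcomes. Build the weights or the imputation from group, TP1 cognition, age and TP1 symptoms, and let these act differently by arm, because arm-specific dropout is what produces the bias.
- If an unweighted GEE is also shown, state a working correlation other than independence.

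The cost is a few sentences and a little more analysis. In the 300-trial simulation the weighted GEE had a standard error of 0.143 against 0.136, about 5% larger (0.143/0.136 = 1.05). No new data are needed. With an exchangeable structure and equal SDs the gain over unweighted GEE is small; the main benefit is that a disagreement between the two methods can then be interpreted.
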